2.2 Specific Aims

AIM 1: To determine if SSI given to during lower extremity fracture surgery reduces post-operative pain. This will be evaluated through the randomizing patients who either receive general or spinal anesthesia into two separate groups, injection or control, and monitoring their pain scores afterwards both in the hospital and outpatient settings. (The type of anesthesia will be determined by the treating anesthesiologist; it is not an experimental variable.)

AIM 2: To determine if SSI given during lower extremity fracture surgery significantly changes post-operative narcotic usage. Using the same groups as above, this will be evaluated through the measurement of narcotic usage both in the immediate post-operative period and for 2 weeks after surgery.

AIM 3: To determine if SSI given during lower extremity fracture surgery alters post-operative function, length of stay, and complications after surgery. This will be measured through rehabilitation documentation, discharge documentation, chart review, and patient interviews.

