Physical therapy records with regards to ambulation distance and exercise endurance will be examined. Daily assessments of pain via VAS will be obtained by the nursing staff as per standard protocol. APS-POQ form will be given on POD1.

After discharge subjects will receive a 7-10 day prescription for acetaminophen 1000mg every 8 hours, meloxicam 15mg oral once daily, and tramadol 50mg oral, every 4-6 hours, PRN (12 tablets to be dispensed). Subjects will call the provider to request refills as needed.

CONFIDENTIAL

This material is the property of the NYU School of Medicine and Langone Medical Center. Do not disclose or use except as authorized in writing by the study sponsor

Interventional Template Version: 28 APR 2017

[figure not shown]
After discharge the research staff will call the subjects up to every other day for the first week, twice in the second week, once weekly for the third and 4th weeks and then monthly after discharge to ascertain pain level, reported narcotic usage, and functional status. Research staff will verify documented narcotic refills through epic and pharmacy records. Four to eight weeks after injury subjects will complete a SMFA as well as another APS-POQ form over the phone with a trained interviewer.

	Pre-op	Post-op: Inpatient	Post-op: Discharge
Standing	Acetaminophen 1gm, oral (every 6-8 hours, not to exceed 4gm daily, review liver function prior to administration)	Acetaminophen 1gm, oral (every 6-8 hours, not to exceed 4gm daily, review liver function prior to administration)	Acetaminophen 1gm, oral (every 6-8 hours, not to exceed 4gm daily, review liver function prior to administration)
	Meloxicam 15mg oral, once daily	Ketorolac 30mg inj, once daily in AM, starting POD1 (15mg>65 years of age and/or renal impairment) Pregabalin (Lyrica) 50mg, oral every 8 hours (hold for sedation)	Meloxicam 15mg oral, once daily
Mild		Ice Therapy PRN (alternating 15 min on/off for skin evaluation)	
Moderate		Tramadol 50mg oral, every 8 hours, PRN	
Severe		Tramadol 100mg, oral, every 8 hours, PRN	
Breakthrough		Oxycodone 5mg, oral every 6 hours, PRN	Tramadol 50mg oral, every 4-6 hours, PRN (12 tablets to be dispensed)

CONFIDENTIAL

This material is the property of the NYU School of Medicine and Langone Medical Center. Do not disclose or use except as authorized in writing by the study sponsor
Interventional Template Version: 28 APR 2017

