4.2 Exclusion Criteria

An individual who meets any of the following criteria will be excluded from participation in this study:

1. Pregnant women
2. Treatment with Arthroplasty
3. Patients who receive a peripheral nerve block
4. Patients who receive intra-op or post-op ketamine
5. Patients with concomitant TBI or MR
6. Polytrauma patients
7. Pathologic Fractures
8. Patients with a contraindication to any of the medications on the study list due to other medical problems such as renal or liver disease or due to allergy/intolerance
9. Patients with prior extremity weakness resulting from stroke or other neurological condition
10. Prior or current history of narcotic use
11. Patients with advanced dementia
12. NYUMC Students, Residents, Faculty

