6.2 Analysis of Endpoints

Primary Endpoints:

amount (mg) of narcotics (oral morphine mg equivalents) used
duration of narcotic use
patient reported pain scores

Secondary Endpoints:

length of stay
progress with physical therapy: distance ambulated, range of motion, exercises done
reported long-term narcotic use at home/SAR
discharge location: home, acute rehab, skilled nursing facility
documented narcotic refills
falls
adverse events

The analysis of narcotic Use, VAS, APS-POQ, and SMFA scores will rely on a univariate repeated-measures analysis of variance model for mean score. This model is in the class of models commonly known as a unirep-ANOVA models. It assumes that the mean score is a function of elapsed time and the treatment regimen assigned. This model takes into account the fact that the subject's repeated measures are correlated. The fitted model will provide statistical estimates of the mean levels, the treatment-effect differences between mean levels, the standard deviation, the intra-class correlation coefficient, 95% CIs, standard errors (SE), and statistical hypothesis tests. The estimates of means will be used to compute summary criteria such as area under the curve (AUC) for each regimen. All estimates reported will be presented their 95% CIs.

CONFIDENTIAL

This material is the property of the NYU School of Medicine and Langone Medical Center. Do not disclose or use except as authorized in writing by the study sponsor

Interventional Template Version: 28 APR 2017

All endpoints will be evaluated as fits the data set with graphical figures such as scatter plots, box-and-whisker plots, and frequency histograms to visualize the distribution of these outcomes and their relationships to covariates and treatment assignment. When appropriate descriptive graphical and tabular methods, and Kaplan-Meier curves will also be estimated and presented in a graphical figure.

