6.2.1 Baseline Descriptive Statistics

The following patient data will be recorded: age, gender, height, weight, date of admission, date of discharge, injury time, injury type, laterality, surgical approach, implants used, duration of surgery, time to union, contamination, ASA, comorbidities (smoking, cardiac history, diabetes, etc.), CBC (WBC, PCV, HGB, RBC, indices, platelet count, differential), and medications.

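### Pre-fracture residence and walking status are not on the baseline list, so discharge location, walking distance and the SMFA are compared with avoidable dilution and loss of precision

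*Combined protocol and SAP*

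**What the plan says.** Aim 3 in section 2.2 covers post-operative function, length of stay and complications. Of its data sources it says: "This will be measured through rehabilitation documentation, discharge documentation, chart review, and patient interviews".

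Section 6.2 lists two relevant secondary endpoints: "discharge location: home, acute rehab, skilled nursing facility" and "progress with physical therapy: distance ambulated, range of motion, exercises done". Section 3.1 gives the source of the walking data: "Physical therapy records with regards to ambulation distance and exercise endurance will be examined". It also sets the only SMFA assessment: "Four to eight weeks after injury subjects will complete a SMFA as well as another APS-POQ form over the phone". No pre-injury or recalled SMFA is planned.

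The baseline list in 6.2.1 opens with "age, gender, height, weight, date of admission, date of discharge, injury time, injury type, laterality, surgical approach, implants used, duration of surgery" and goes on to union, contamination, ASA, comorbidities, blood count and medications. It does not include where the patient lived or how the patient walked before the fracture.

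Section 4.1 sets no residence or walking criterion. Section 4.2 excludes "Patients with prior extremity weakness resulting from stroke or other neurological condition" and patients with advanced dementia. Section 4.4 adds a capacity test and an orientation check, and speaks of excluding dementia generally.

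Randomisation is within anaesthesia type only (6.4). The repeated-measures model in 6.2 covers narcotic use, VAS, APS-POQ and SMFA, and has time and treatment as its only terms. No analysis is specified for discharge location or walking distance.

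**The concern.** After a hip or femoral shaft fracture, where a patient goes on discharge and how far the patient walks depend heavily on residence and mobility beforehand. A mentally intact facility resident, or someone who did not walk because of arthritis or frailty, can be eligible. If the resident goes back to the facility, the discharge category is the same as for a patient who lived at home and lost independence. The prior non-walker contributes a distance near zero in either arm.

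These results are largely settled before randomisation. Pooled with everyone else's, they pull the arm difference toward zero; for walking distance they also widen the spread. Aim 3 would then be answered with less precision than the same patients could give. Section 2.3 raises the stakes, because it would read a failure to reject the null as showing no clinically relevant effect on post-operative outcomes.

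**Working it through.** **Is the information collected or made unnecessary elsewhere?** Sections 2.2, 3.1, 4.1, 4.2, 4.4, 6.2, 6.2.1 and 6.4 were set side by side. None lists pre-fracture residence, walking ability or walking aid. The open-ended *etc.* in 6.2.1 sits inside the comorbidity bracket and does not plausibly cover them. No eligibility rule makes them redundant.

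**Figures in the plan.** The plan gives no rate, effect size or power for these endpoints, so there is no figure of its own to reproduce. The sample size in 6.3 is for daily narcotic use and is not used here.

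**Illustration: discharge home.** From the plan: 200 per arm (100 per arm in each of two anaesthesia cohorts, section 3) and 300–350 evaluable (4.6), so 150 per arm at the low end. Assumed, because the documents give no rates:
- 45% v 60% go home among patients admitted from home;
- no prior facility resident is discharged home in either arm;
- prior residents are a share f of 5–20% of the sample;
- discharge is analysed as home or not home, with a two-sided test at 0.05.

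All patients: p1 = 0.45(1−f), p2 = 0.60(1−f), n = N per arm. 
Restricted to patients admitted from home: p1 = 0.45, p2 = 0.60, n = N(1−f) per arm. 
z = (p2−p1) / √{[p1(1−p1) + p2(1−p2)]/n}; power = Φ(z − 1.96).

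Example, f = 15%, N = 200:
- All patients: 0.3825 v 0.51, difference 0.1275. SE = √{(0.2362 + 0.2499)/200} = 0.0493, z = 2.59, power 0.73.
- Restricted: 0.45 v 0.60, n = 170. SE = √{(0.2475 + 0.24)/170} = 0.0536, z = 2.80, power 0.80.

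| f | Difference, all patients | Power restricted v all, 200 per arm | Power restricted v all, 150 per arm | Ratio of squared z |
|---|---|---|---|---|
| 5% | 14.3 points | 0.84 v 0.82 | 0.73 v 0.70 | 1.06 |
| 10% | 13.5 points | 0.82 v 0.78 | 0.70 v 0.66 | 1.11 |
| 15% | 12.8 points | 0.80 v 0.73 | 0.68 v 0.61 | 1.17 |
| 20% | 12.0 points | 0.78 v 0.69 | 0.65 v 0.56 | 1.23 |

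The last column says that the restricted comparison is worth 6–23% more patients, although it uses fewer. With 50% v 65% assumed instead, the pattern is the same: at 200 per arm, 0.84 v 0.82 at f = 5% and 0.78 v 0.67 at 20%.

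**Side check: walking distance.** Assume an effect of 0.3 SD among walkers, a mean of 1.5 SD, and zero distance for a share f of non-walkers. The difference becomes 0.3(1−f), and the variance (1−f) + f(1−f)×1.5². At f = 10% these are 0.27 and 1.1025, a standardised effect of 0.27/1.05 = 0.257. With 200 per arm, power is 0.73 for all patients against 0.81 among walkers only. At f = 5% it is 0.79 against 0.83. These inputs are also assumptions. No figure is offered for the SMFA.

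**The case against.** Several points on the other side stand.

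A reader might infer that the plan counts a nursing facility as a poor outcome. It does not: 6.2 lists three destinations with no ordering, score or dichotomy, and the home/not-home comparison above is an assumption of this check.

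A reader might also infer that a chance imbalance in prior residents would bias the result and could never be examined. Under the assumptions above, the 95% range for such an imbalance, 1.96√{2f(1−f)/N}, is about ±4 points (f = 5%, 200 per arm) to ±9 points (f = 20%, 150 per arm). That is ordinary sampling variation, which standard errors and the type I error rate already cover. Nor is the information shown to be lost: Aim 3 names chart review and interviews as sources, so both items could be extracted later. The gap is in what is planned for extraction and analysis. The as-treated approach in 6.1 could weaken the protection of randomisation if patients do not receive their allocation, but the documents give no rate for that.

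The share of affected patients may be small. Besides the exclusions for neurological weakness and advanced dementia, the capacity and orientation screen in 4.4 removes some facility residents, and the exclusions for medical contraindications, narcotic history and arthroplasty may remove more. The documents do not say how many remain.

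Covariate adjustment is not ruled out either. The Protocol Summary lists linear regression, and 6.2 mentions relationships to covariates, though only for graphical display. Neither helps with a covariate that is not listed for collection.

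Finally, the assumed 15-point effect on discharge may be generous for an injection whose main benefit section 2.4 expects in the first day or two.

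**Conclusion.** The omission is real, and it costs precision. Discharge location, distance ambulated and the SMFA bear on the function question in Aim 3 (the Aim does not name the SMFA; that link is inferred), yet pre-fracture residence and walking status are neither listed for collection nor used.

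The size depends wholly on assumed rates. For discharge home with 200 per arm, the loss is about 2 points of power if prior residents are 5% of the sample, about 7 at 15% and about 9 at 20%. At the low end of that range the loss is negligible.

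The documents do not support a claim of systematic bias, because allocation is randomised. They do not support a threat to the primary pain and narcotic endpoints either, which are not directly affected. This is a minor-to-moderate point about secondary and supportive outcomes, worth acting on because the remedy is cheap.

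**What to change.** 1. In 6.2.1, add pre-injury residence (home or facility) and pre-injury walking status (independent, with aid, non-ambulatory), taken from the admission note as recorded before randomisation.
2. In 6.2, define the discharge comparison as discharge home among patients admitted from home, and show prior facility residents separately. For patients admitted from home this is the same as return to prior residence. Scoring return to prior residence over all patients would not remove the dilution: prior residents who all go back would count as successes in both arms, and the difference would still be 15(1−f) points.
3. In 6.2, include pre-injury walking status as a covariate for distance ambulated and the SMFA.

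Both items are fixed before randomisation, so restricting or adjusting on them creates no post-randomisation selection. The cost is two chart fields, a few sentences in the analysis section and a somewhat smaller denominator for one secondary endpoint. Sample size, visits and treatment do not change.

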2.3 Statistical Hypotheses

We hypothesize that SSI given at the time of surgery will reduce post-operative pain and narcotic usage not only during the patients' inpatient hospital stay but also as an outpatient. Furthermore, SSI will improve post-operative function, shorten length, of stay, and reduce complications not limited to but including deep venous thrombosis, delirium, and narcotic dependency. Failing to reject the null hypothesis would signify that SSI has no clinically relevant impact on post-operative outcomes in hip fracture surgery.

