SAE	Serious adverse event
IV	Intravenous
PO	Taken orally
PRN	Taken as needed
TID	Taken three times per day
Q4h	Taken every four hours
CI	Confidence interval
SD	Standard deviation; a parameter which characterizes a population distribution
SE	Standard error
SSI	Surgical Site Injection
ANOVA	analysis of variance; a linear model
NSAID	Non-steroidal anti-inflammatory drug
LOS	Length of Stay

CONFIDENTIAL

This material is the property of the NYU School of Medicine and Langone Medical Center. Do not disclose or use except as authorized in writing by the study sponsor
Interventional Template Version: 28 APR 2017

Protocol Summary

Title	Effects of a Surgical Site Injection on Pain Scores and Narcotic Use after Orthopedic Trauma Surgery
Short Title	Understanding and Improving post-operative Pain in the Fracture Population
Brief Summary	This is a phase I, randomized, single-blind, placebo-controlled, single-center study of the effects of surgical site injection on pain and narcotic utilization in participants who undergo surgery for lower extremity fractures. 400 participants with lower extremity fractures who are admitted for operative fixation will be included in the study. Participants will be randomized to receive either a pain cocktail injection around the fracture site and surrounding tissues or control (no injection). An analysis of pain scores, rehabilitation progress, length of stay, narcotic utilization, and satisfaction scores will be performed.
Phase	Clinical study phase 1
Objectives	To understand the effect of surgical site injections of post-operative pain control
Methodology	phase I, randomized, single-blind, placebo-controlled, single-center study
Endpoint	10mg change in narcotic utilization daily or 15mm change in VAS
Study Duration	4 years
Participant Duration	3 months
Duration of IP administration	Once during surgery
Population	400 participants with peritrochanteric fractures
Study Sites	NYU Langone (Kimmel, Tisch, Langone Orthopedic Hospital, Lutheran)
Number of participants	400
Description of Study Agent/Procedure	Peri-incisional injection of 40cc 0.25% bupivacaine, 5 mg morphine sulfate (1 mg/cc, 5 cc total), and 30 mg of ketorolac (30 mg/cc, 1 cc total) into soft tissue and musculature surrounding the fracture site and 0.25% Marcaine 10 mL into the subcutaneous tissue surrounding the surgical incision.
Reference Therapy	Reference is a control
Key Procedures	Surgical Site injection

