2.4 Objectives and Purpose

The ultimate goal of this study is to determine how effective SSI is in reducing post-operative pain in patients with lower extremity long bone fractures and to determine how that reduction in post-operative pain impacts a patient's hospital stay in the short term and their use of narcotics during the treatment period. Primary outcomes measures will be reported and observed pain scores and narcotic use. VAS and APS-POQ will be used to measure pain scores. While it is expected that the greatest benefit of the SSI will be seen in the first day or two after surgery it is possible that there will be an overall reduction in long-term narcotic use. Secondarily, function/rehabilitation, length of stay, and complications may be impacted by the intervention.

CONFIDENTIAL

This material is the property of the NYU School of Medicine and Langone Medical Center. Do not disclose or use except as authorized in writing by the study sponsor

Interventional Template Version: 28 APR 2017

3 Study Design and Endpoints

Cohort A: Spinal Anesthesia	ARM 1: Experimental	Sample Size: 100	SSI
	ARM 2: Control	Sample Size: 100	No intervention

Cohort B: General Anesthesia	ARM 1: Experimental	Sample Size: 100	SSI
	ARM 2: Control	Sample Size: 100	No intervention

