4.6 Total Number of Participants and Sites

Recruitment will end when approximately 400 participants are enrolled. It is expected that approximately 400 participants will be enrolled in order to produce 300-350 evaluable participants. There were 350 procedures done on patients matching the inclusion and exclusion criteria in the last year. Based on the simplicity of the intervention and historical enrollment for patients undergoing orthopedic surgery, we anticipate at least 25% participation.

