6.3 Sample Size

In order to have a sufficient N to power the study a minimum of 200 subjects per anesthesia group will be recruited ($\alpha=0.05$, $\beta=0.2$). If the difference in the morphine equivalent consumption, is found to be 15mg daily with a standard deviation between the groups of 25mg, we will need 90 subjects per group in order to reject the null hypothesis with the probability (power) 0.8. The Type I error probability associated with this test of this null hypothesis is 0.05. To allow for within group analyses and accommodate for the poor follow-up rate in fracture patients we will need 400 patients.

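### Section 2.3 reads a non-significant result as proof of no clinically relevant effect, which a superiority test without a margin cannot show

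*Combined protocol and SAP*

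**What the plan says.** Section 2.3 predicts that SSI will lower pain and narcotic use, in hospital and afterwards, improve function, shorten stay and "reduce complications not limited to but including deep venous thrombosis, delirium, and narcotic dependency". It closes with the rule for a null result: "Failing to reject the null hypothesis would signify that SSI has no clinically relevant impact on post-operative outcomes in hip fracture surgery".

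Section 2.2 (Aim 3) likewise asks whether SSI "alters post-operative function, length of stay, and complications after surgery".

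The sample size in section 6.3 covers one outcome: "If the difference in the morphine equivalent consumption, is found to be 15mg daily with a standard deviation between the groups of 25mg", with alpha 0.05 and power 0.8. The Protocol Summary lists a different change under Endpoint: "10mg change in narcotic utilization daily or 15mm change in VAS". Neither figure is called a margin for judging a null result.

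Section 6.2 promises estimates with 95% CIs and hypothesis tests, but does not link the intervals to the reading of a null result. Section 5.2 allows that the study may turn out inconclusive.

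**The concern.** A non-significant superiority test means the data did not show a difference. It does not show that any difference is too small to matter. That needs a confidence limit that excludes a stated relevant difference, and the documents set no such rule.

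The sentence is also broad. It speaks of post-operative outcomes in general, directly after a list that includes function, length of stay, deep venous thrombosis, delirium and narcotic dependency. None of these has a power calculation, nor do two of the three primary endpoints in section 6.2 (duration of narcotic use and pain scores). Followed as written, the protocol would permit a report that SSI has no relevant effect on outcomes for which the trial may have had little chance of seeing one.

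**Working it through.** **Inputs.** Alpha 0.05 and power 0.8 (section 6.3; two-sided assumed, since sidedness is not stated). Difference 15 mg, SD 25 mg (section 6.3). Change of 10 mg (Protocol Summary). Each arm of each anesthesia cohort is listed as "Sample Size: 100" (section 3), so 200 per arm pooled. Section 4.6 enrolls 400 "in order to produce 300-350 evaluable participants"; with equal cohorts that is 75-87.5 per arm per cohort and 150-175 per arm pooled.

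**The plan's own figure.** A two-sample t-test for 15 mg with SD 25 needs 44.6, so 45 per arm, or 90 for both arms. The stated 90 per group therefore reproduces if a group is one anesthesia cohort with both arms. As 90 per arm it would need a per-arm SD of about 25 × √2 = 35.4 mg (88 per arm).

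**Narcotic use.** SE = 25 × √(2/n), with power from the noncentral t. A result exactly on the significance boundary has an observed difference of t × SE, so its upper 95% limit is 2 × t × SE. For n = 75: SE = 4.08, t = 1.976, boundary 8.07 mg, upper limit 16.1 mg.

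| n per arm | Setting | 10 mg missed | 15 mg missed | Upper 95% limit if just non-significant |
|---|---|---|---|---|
| 75 | cohort, 300 evaluable | 31.8% | 4.5% | 16.1 mg |
| 87.5 | cohort, 350 evaluable | 25.1% | 2.3% | 14.9 mg |
| 100 | cohort, all 400 | 19.6% | 1.2% | 13.9 mg |
| 150 | pooled, 300 evaluable | 6.8% | 0.06% | 11.4 mg |
| 175 | pooled, 350 evaluable | 3.8% | 0.01% | 10.5 mg |
| 200 | pooled, all 400 | 2.1% | 0.003% | 9.8 mg |

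Non-significance alone excludes 10 mg only in the last row: all 400 evaluable, pooled, with an SD of 25.

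*Sensitivity.* If 25 mg is a single-day SD and k days are averaged, SD = 25 × √((1 + (k−1) × ICC)/k). With k = 2-3 and an assumed intra-class correlation (ICC) of 0.3-0.7, the per-cohort miss rate for 10 mg falls to 3-25%. If the per-arm SD is instead 35, it rises to about 48% at 100 per arm and 18.5% at 200 (normal approximation).

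**Complications.** The documents give no rates, so the control rates and the halving are assumptions. With p̄ the mean of the two rates, SE0 = √(2p̄(1−p̄)/n), SE1 = √((p1(1−p1) + p2(1−p2))/n) and power = Φ((p1 − p2 − 1.96 × SE0)/SE1). For 10% vs 5% at n = 175: SE0 = 0.0282 and SE1 = 0.0280, so power = Φ(−0.185) = 0.427 and the miss rate is 57%.

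| Control vs SSI (assumed) | Missed, n = 150 | n = 175 | n = 200 |
|---|---|---|---|
| 5% vs 2.5% | 79% | 77% | 74% |
| 10% vs 5% | 62% | 57% | 52% |
| 20% vs 10% | 32% | 25% | 20% |

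**Function and length of stay.** Pooled power is 80% for a standardized difference of 0.325, 0.300 or 0.281 SD at 150, 175 or 200 per arm. Whether that is small enough cannot be judged, because no relevant difference or SD is given. Low power is not shown here; what is missing is any difference to exclude.

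**The case against.** The strongest reply is that the sentence does no work. It is one line of hypothesis narrative, and no test, estimate, sample size or stopping rule in section 6 or section 4.8 uses it. The planned 95% CIs would show readers which effects remain possible, and section 5.2 shows that the authors accept an inconclusive outcome. All of this lowers the risk, but none of it is tied to section 2.3, which remains the only stated rule for reading a null result.

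On the numbers, the sized outcome is well covered when pooled. The larger miss rates need separate tests within each anesthesia cohort. The section 6.2 model has no anesthesia term, although sections 3 and 6.3 size by cohort. The figures also use a single-measure t-test in place of the planned repeated-measures model. These points stand, and the narcotic figures are illustrations. The complication figures rest on assumed rates and span 20% to 79%; that stands too.

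The sentence could also be read as referring only to the narcotic null, the one with stated error rates. Its reference to outcomes in general, straight after the list of function, stay and complications, favors the wider reading. Even on the narrow reading, non-significance does not exclude 10 mg at the protocol's own evaluable numbers.

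**Conclusion.** The concern holds and should be fixed. The flaw is one of logic and depends on no power figure. Its practical size varies by outcome:

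- **Narcotic use:** small when pooled or at 15 mg, and sizeable only for 10 mg within one cohort (20-32% missed), given SD 25 and a single-measure test.
- **Complications:** potentially large. A halving is missed more often than not at assumed control rates of 5-10%, even with all 400 evaluable.
- **Function and length of stay:** no conclusion of no effect is possible without a stated difference.

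The planned analysis itself is unaffected. What changes is what the trial may claim after a null result.

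**What to change.** Replace the last sentence of section 2.3 with:

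> A non-significant result will be reported as not demonstrating a difference. Absence of a clinically relevant benefit will be concluded only if the 95% CI for the SSI-control difference excludes the prespecified relevant difference for that outcome, and will not be concluded for outcomes without one.

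Then designate the relevant difference for narcotic use (the Summary has 10 mg, section 6.3 is powered on 15 mg; the two need not be equal, but one must be named for this purpose) and for VAS (the Summary has 15 mm).

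The cost is one sentence and two decisions. The downside is that more null results will be labelled inconclusive. If the true difference is zero, the chance that the 95% CI excludes a 10 mg benefit equals the power to detect 10 mg: 68-75% per cohort at 75-87.5 per arm (80% at 100) and 93-96% pooled at 150-175 (98% at 200). For 15 mg it is 95-99% per cohort and over 99.9% pooled. A supported null conclusion therefore stays within reach for narcotic use.
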